5.9. Pharmacokinetic/Pharmacodynamic Analyses

Pharmacokinetic/pharmacodynamics (PK/PD) analyses will be conducted by PK/PD group.

5.10. Safety Analyses

Safety measures will include AEs, vital signs, hypoglycemic episodes, treatment exposure, adjudicated cardiovascular events, laboratory measurements, electrocardiograms (ECGs) and immunogenicity. Safety analysis will be reported for the Safety Population using data measured while on treatment and after study drug discontinuation. Unless otherwise specified, the comparison will be between LY3209590 (by pooling LY3209590 Algorithm 1 and LY3209590 Algorithm 2) and insulin degludec.

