Approximately 238 participants will be randomly assigned to study intervention such that approximately 190 evaluable participants complete the study.

Intervention Groups and Duration:

Participants will be randomized in a 1:1 ratio to receive the interventions listed below:

[figure not shown]
- LY3209590 subcutaneously weekly, dosed per Algorithm 1
- Insulin degludec subcutaneously daily, dosed per a modified Riddle algorithm

The maximum total duration of study participation for each participant is up to 33 weeks, across the following study periods:

- Study Period 1: screening and lead-in period, approximately 2 weeks
- Study Period 2: treatment period, 26 weeks
- Study Period 3: safety follow-up period, 5 weeks

Data Monitoring Committee: No

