9.2. Sample Size Determination

Approximately 238 participants will be randomized to study treatment (LY3209590 Algorithm 1, and insulin degludec) such that approximately 119 participants will be randomized to each treatment. Assuming a 20% dropout rate, approximately 190 participants will complete the study (approximately 95 participants per treatment group).

The 190 participants who complete the treatment will provide at least 80% statistical power to demonstrate the noninferiority in the change in HbA1c from baseline to 26 weeks for LY3209590 Algorithm 1 versus insulin degludec, based on the following assumptions:

- True mean difference = 0%
- SD of 1.1%
- NIM of 0.4%
- Using 2-sided alpha level of 0.1

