10.12. Appendix 12: Protocol Amendment History

The Protocol Amendment Summary of Changes Table for the current amendment is located directly before the Table of Contents (TOC).

Amendment [c]: 14 August 2020

This amendment is considered substantial based on the criteria set forth in Article 10(a) of Directive 2001/20/EC of the European Parliament and the Council of the European Union.

Overall Rationale for the Amendment:

The amendment provides information to reflect and reinforce investigational medical device requirements absent in the initial study protocol for Algorithm 2. These requirements are consistent with country regulations where Algorithm 2 will be used.

Section # and Name	Description of Change	Brief Rationale
Section 1.1. Synopsis Section 1.2. Schema Section 4.1.1. Study Visits Section 6.1. Study Interventions(s) Administered	Addition of language regarding randomization	Clarify that randomization distribution may vary based on country due to removal of randomization into LY3209590 Algorithm 2 (digital) treatment for the European Union (EU)
Section 1.3 Schedule of Activities	Addition of product complaint review in AE/SAE review	Product complaint review was added to ensure alignment with Lilly guidance
Section 2.3. Benefit/Risk Assessment	Addition of language related to LY3209590 Algorithm 1 (paper) and LY3209590 Algorithm 2 (digital)	Additions to clarify regulatory designation of LY3209590 Algorithm 1 (paper) and LY3209590 Algorithm 2 (digital)
Section 2.3.1. Protocol Risk Mitigation Features for Investigational Algorithm 2	Addition of language for protocol risk mitigation	Summarization of key risk mitigations for the protocol including investigational medical device
Section 4.1.1. Study Visits	Updated wording describing Algorithm 2	Clarification of Algorithm 2 as an investigational individualized accruing data algorithm
Section 6.1. Study Interventions(s) Administered	Addition of language describing Algorithm 1 and Algorithm 2	Clarification and description of algorithms
Section 6.1.2.3. Management of Patients with Severe, Persistent Hyperglycemia during Treatment Period	Addition of language related to transient hyperglycemia	Provide acknowledgment of the potential for transient hyperglycemia and guidance for management during transition period from prestudy basal to LY3209590
Section 6.1.3. Medical Devices	Addition of language for Algorithm 2	Algorithm 2 was added based on regulatory feedback and classification as a medical device

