5.10.2. Adverse Events

Adverse events will be summarized as TEAEs (defined as events that are newly reported after the first dose of study basal insulin or reported to worsen in severity from baseline) and compared between treatments unless otherwise specified. The Medical Dictionary for Regulatory Activities (MedDRA) Lowest Level Term (LLT) will be used in determining the treatment-emergent status. The maximum severity for each LLT during the baseline period will be used as baseline severity. All analysis will be performed on the data collected from the date of first dose of study drug (or the randomization visit date if date of first dose is not available) to the end of the study (up to Visit 801).

The incidence of patients with at least 1 TEAE and the incidence of TEAEs by PT and system organ class (SOC) will be presented by treatment group. The number and percentage of patients

with TEAEs will be summarized by treatment using MedDRA PTs nested within SOC. Events will be ordered by decreasing frequency within SOC.

The number and percentages of patients with TEAEs ($\geq 2\%$ before rounding) will be summarized by treatment using MedDRA PT (without regard to SOC). Events will be ordered by decreasing frequency.

The incidence of participants with at least 1 TEAE assessed as possibly related to the IP will be summarized by treatment group using MedDRA PT nested within SOC. Events will be ordered by decreasing frequency within SOC. In addition, a summary of TEAEs by maximum severity will be presented descriptively by treatment group.

Discontinuations due to AEs will be summarized by PT and compared between treatment groups using Fisher's exact test for the Safety Population.

All SAEs (including death) will be listed by patient for the Safety Population.

Summary of TE-SAEs similar to summaries for the proportion of patients experiencing each reported TEAE by SOC will be included for the Safety Population.

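### The default pooled safety comparison can be confounded by country and enrollment period, and the adverse event summaries have neither a country-stratified analysis nor an Algorithm 1-only column

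*SAP*

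**What the plan says.** **The contrast.** SAP 5.10 (Safety Analyses) states: "Unless otherwise specified, the comparison will be between LY3209590 (by pooling LY3209590 Algorithm 1 and LY3209590 Algorithm 2) and insulin degludec". SAP 5.1 says the same, and Protocol 9.3 builds the pooling into the Safety Population. The exception is the set of safety parameters derived from CGM, which SAP 5.1 restricts to Algorithm 1 versus degludec.

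**Where Algorithm 2 was assigned.** The current design has two arms: "Participants will be randomized in a 1:1 ratio to receive the interventions listed below". Before that, the entry for Amendment c in Protocol 10.12 records that "randomization distribution may vary based on country due to removal of randomization into LY3209590 Algorithm 2", the region concerned being the European Union. The rationale for the current amendment, printed before the table of contents, adds three facts:
- Algorithm 2 dosing had been seen at few sites and in few participants, early on.
- An extension to all US sites was only planned.
- Variation in allocation by country no longer applies.

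These entries are used here as evidence of how participants were allocated, not as text in conflict with the current plan.

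**The tests.** SAP 5.1 makes Fisher's exact test the default for categorical measures. SAP 5.10.2 says: "Discontinuations due to AEs will be summarized by PT and compared between treatment groups using Fisher's exact test". The same test is named for injection site reactions (SAP 5.10.3.4) and systemic hypersensitivity (SAP 5.10.3.5). Treatment-emergent events (TEAEs) are compared between arms, and treatment-emergent serious events (TE-SAEs) are summarized as proportions. None of these is stratified by country.

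**The concern.** Randomization was stratified by country (Protocol 6.3). That balances the arms within each country, but a crude comparison across countries is balanced only if the allocation ratio is the same everywhere. Adding Algorithm 2 participants to the LY3209590 arm raises the LY3209590:degludec ratio only in the countries, and only in the months, where that arm was open. If event risk or event reporting also differs between those countries or months and the rest, part of any difference between pooled LY3209590 and degludec is not due to the drug. The distortion could create a signal or hide one. TE-SAE incidence is a secondary safety endpoint (SAP 4.2.2).

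The SAP protects other analyses against this. The pooled HbA1c comparison in SAP 5.7 reuses a model with a country term, and the CGM safety parameters leave Algorithm 2 out by default. The adverse event summaries have neither protection. The only optional sensitivity analysis that covers safety measures (SAP 5.1) excludes participants who departed from the dose algorithm, which is a different question.

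**Working it through.** **1. The plan's own figure.** The documents give no design figure for the safety comparisons. Protocol 9.2 gives one for HbA1c, used here because it supplies the arm size. Inputs: "Using 2-sided alpha level of 0.1"; "will provide at least 80% statistical power to demonstrate the noninferiority"; "True mean difference = 0"; SD 1.1; margin 0.4; "Assuming a 20% dropout rate, approximately 190 participants will complete the study".

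n per arm = 2 × (1.6449 + 0.8416)² × 1.1² / 0.4² = 2 × 6.183 × 1.21 / 0.16 = 93.5, so 94. With 95 per arm the power is 80.5%. Then 190 / 0.8 = 237.5, so 238 randomized, or 119 per arm. The figure reproduces.

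**2. Country imbalance.** The number on Algorithm 2 and the earlier allocation ratios are not stated. Assumptions: 119 on Algorithm 1 and 119 on degludec with the same country mix; n₂ Algorithm 2 participants on top, all in one country group; that group holds a share u of the others.

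Imbalance = (119u + n₂)/(119 + n₂) − u = n₂(1 − u)/(119 + n₂)

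| u | n₂ = 10 | n₂ = 20 | n₂ = 40 |
|---|---|---|---|
| 0.4 | 6/129 = 4.7 points | 12/139 = 8.6 | 24/159 = 15.1 |
| 0.5 | 5/129 = 3.9 | 10/139 = 7.2 | 20/159 = 12.6 |
| 0.7 | 3/129 = 2.3 | 6/139 = 4.3 | 12/159 = 7.5 |

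**3. Bias for a common event.** Bias = imbalance × difference in event risk between the country groups. No such difference is given. Assuming 40% versus 60% and u = 0.5:
- n₂ = 10: 3.9 × 0.20 = 0.8 points
- n₂ = 20: 7.2 × 0.20 = 1.4 points
- n₂ = 40: 12.6 × 0.20 = 2.5 points

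At n₂ = 20 the arm risks are 0.4 + 0.572 × 0.2 = 0.514 and 0.50. The standard error is √(0.514 × 0.486/139 + 0.5 × 0.5/119) = 0.062, or about 6 points, so the bias is 0.23 standard errors.

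By normal approximation, the type I error at a nominal 10% is 10.3%, 10.9% and 12.9% for the three sizes. Fisher's test, simulated with 6,000 runs at u = 0.5, rejects in 8.0% with no Algorithm 2 participants, 8.0% with 20 and 11.2% with 40.

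Over a wider assumed range (n₂ from 5 to 40, u from 0.3 to 0.7, risk gap 10 or 20 points), the bias is 0.1 to 3.5 points and the approximate type I error 10.0% to 15.7%. At the worst corner (u = 0.3, n₂ = 40, 40% versus 60%) the simulated Fisher rate is 13.7%.

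**4. Bias for a rare event.** Assuming 5% versus 10%, u = 0.5 and n₂ = 20, the bias is 7.2 × 0.05 = 0.36 points. The standard error is √(0.0786 × 0.9214/139 + 0.075 × 0.925/119) = 0.033, or 3.3 points. The bias is about 0.11 standard errors.

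**5. Could the earlier ratios have removed the imbalance?** A country with three arms matches a 1:1 two-arm country on the pooled ratio only if degludec received as many participants as both LY3209590 arms together. In that case Algorithm 1 versus degludec is unequal there. A country-stratified comparison is valid in either case; the crude pooled one is free of country imbalance only in the favorable case.

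**The case against.** A reader might infer that the pooled comparison *is* confounded. The documents do not show that. Confounding needs a pooled ratio that differs by country and event risk that differs by country. The ratios before the current amendment are not stated, and the amendment entry says only that the distribution may vary. Nothing in either document says that adverse event risk or reporting differs between countries. This objection stands, and the point is therefore worded as a possibility.

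A reader might also multiply the largest imbalance by a 30-point country gap and report a bias of 4.5 points (15.1 × 0.30). That needs 40 Algorithm 2 participants, where the rationale speaks of few, and a gap with no source. It would not suit serious events if these are uncommon. Nor do the documents say that Algorithm 2 was used only in the US, or that no EU participant received it before Amendment c.

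Two further points are fair. SAP 5.3 tabulates country and region by arm for the Safety Population, so an imbalance would be visible; but showing it does not adjust for it. And early use at few sites can bring site and calendar-time differences that country strata do not remove. That limits the remedy without making the crude test better.

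**Conclusion.** The concern holds as a possible bias of unknown but probably small size. The default pooled safety comparison can be confounded by country and enrollment period, and the plan does not adjust for this in the adverse event summaries.

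On the assumptions stated, with 10 to 40 Algorithm 2 participants in one country group holding 40% to 70% of the others, the country share differs between arms by about 2 to 15 points. With few Algorithm 2 participants, the bias for a common TEAE is small against a standard error of about 6 points; for rare serious events it is much smaller in absolute terms. The sizes rest on three inputs that the documents do not give: the number on Algorithm 2, the earlier allocation ratios and event risk by country. This is a cheap improvement and not a defect that undermines the safety evaluation.

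**What to change.** In SAP 5.10, for the overall summaries only (any TEAE, any TE-SAE, discontinuation due to an adverse event, injection site reactions, systemic hypersensitivity):

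1. For pooled LY3209590 versus degludec, give a Mantel-Haenszel risk difference with its 90% confidence interval, stratified by country. Use US/non-US, a split already defined in SAP 5.12, where country strata are too thin. Use an exact stratified test where events are few.
2. Show Algorithm 1 versus degludec in an adjacent column. This is supporting information, because its own balance by country also depends on the unstated earlier ratios.
3. Leave sparse preferred-term tables descriptive.

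The cost is SAP wording and a little more output, with no new data and no change to the primary analysis. The downsides are sparse strata for rare events and residual site or calendar-time differences that country strata cannot remove; the report should say so.

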5.10.1. Study Drug Exposure

Exposure in days in the study will be calculated for each patient and summarized by treatment group. Exposure during the treatment period will be calculated from date of first study basal insulin dose collected in the electronic case report form (eCRF) to date of discontinuation from study treatment (i.e., the last dose date for insulin degludec, and the last dose date + 7 days for LY3209590). The sum of exposure in total patient years will also be provided.

Frequency of subjects falling into the following different exposure ranges will also be summarized: >0 days, ≥ 7 days, ≥ 14 days, ≥ 30 days (1 month), ≥ 60 days (2 months), ≥ 90 days (3 months), ≥ 120 days (4 months), ≥ 183 days (6 months) days.

In addition, the duration of follow-up in days for each individual patient is calculated from the date of last dose of study drug for insulin degludec or the date of last dose of study drug + 7 days for LY3209590 to the last study visit date. The duration of the follow-up in days will be summarized (n, mean, standard deviation, minimum, maximum median, and sum in total patient years) by treatment group.

The duration on study from date of the first study drug to the last study visit date (including the follow-up visit) will also be summarized by treatment group, the following summary statistics will be provided: n, mean, standard deviation, median, minimum, maximum, and sum in total patient years.

A by-patient listing of drug exposure data will be created to provide data for the CSR.

5.10.2. Adverse Events

Adverse events will be summarized as TEAEs (defined as events that are newly reported after the first dose of study basal insulin or reported to worsen in severity from baseline) and compared between treatments unless otherwise specified. The Medical Dictionary for Regulatory Activities (MedDRA) Lowest Level Term (LLT) will be used in determining the treatment-emergent status. The maximum severity for each LLT during the baseline period will be used as baseline severity. All analysis will be performed on the data collected from the date of first dose of study drug (or the randomization visit date if date of first dose is not available) to the end of the study (up to Visit 801).

The incidence of patients with at least 1 TEAE and the incidence of TEAEs by PT and system organ class (SOC) will be presented by treatment group. The number and percentage of patients

with TEAEs will be summarized by treatment using MedDRA PTs nested within SOC. Events will be ordered by decreasing frequency within SOC.

The number and percentages of patients with TEAEs ($\geq 2\%$ before rounding) will be summarized by treatment using MedDRA PT (without regard to SOC). Events will be ordered by decreasing frequency.

The incidence of participants with at least 1 TEAE assessed as possibly related to the IP will be summarized by treatment group using MedDRA PT nested within SOC. Events will be ordered by decreasing frequency within SOC. In addition, a summary of TEAEs by maximum severity will be presented descriptively by treatment group.

Discontinuations due to AEs will be summarized by PT and compared between treatment groups using Fisher's exact test for the Safety Population.

All SAEs (including death) will be listed by patient for the Safety Population.

Summary of TE-SAEs similar to summaries for the proportion of patients experiencing each reported TEAE by SOC will be included for the Safety Population.

5.10.3. Adverse Events of Special Interest (AESI)

Summary and analysis of TEAEs related to the following adverse events of special interest (AESIs) is specified in this section:

- deaths and nonfatal cardiovascular events
- hypoglycemia events
- hepatobiliary events
- injection site reactions
- systematic hypersensitivity reactions

5.10.3.1. Death and Nonfatal Cardiovascular Events

Deaths and nonfatal cardiovascular AEs will be adjudicated by an independent Clinical Endpoint Committee with cardiology expertise. The following events will be adjudicated and listed by patient for all the Safety Population: death due to cardiovascular events, myocardial infarction, hospitalization for unstable angina, hospitalization for heart failure, coronary interventions (such as coronary artery bypass graft or percutaneous coronary intervention), and cerebrovascular events, including cerebrovascular accident (stroke) and transient ischemic attack. The actual term and PT of the event, date of first dose and last dose of study drug, result of adjudication, and time from first dose to event will be listed.

5.10.3.2. Hypoglycemia Events

According to 2020 American Diabetes Association standard of medical care in diabetes, there are two levels of hypoglycemia defined by glucose concentration:

- Level 1: glucose < 70 mg/dL (3.9 mmol/L) and glucose ≥ 54 mg/dL (3.0 mmol/L)
- Level 2: glucose < 54 mg/dL (3.0 mmol/L)

With the above glucose reading requirement for Level 1 and 2 hypoglycemia, the following type of hypoglycemia events will be derived: documented hypoglycemia, documented nocturnal hypoglycemia (occurs between bedtime and waking), and documented non-nocturnal hypoglycemia (occurs between waking and bedtime).

Per the study protocol, severe hypoglycemia is reported as a serious AE. Severe hypoglycemia is defined in the protocol and is consistent with the ADA definition, but also requires investigator confirmation of neurological impairment. The 2020 American Diabetes Association standard of medical care in diabetes also classified severe hypoglycemia as Level 3 hypoglycemia. During a severe hypoglycemia episode, the participant has an altered mental status and cannot assist in his/her own care, may be semiconscious or unconscious, or experience coma with or without seizures, and may require assistance of another person to actively administer carbohydrate, glucagon, or other resuscitative actions. This information will be collected in the patient eDiary and the severe hypoglycemia will be analyzed.

Table BDCP.1 provides the summary of statistical method for hypoglycemia event related analysis. Additionally, severe hypoglycemia events will be listed, and incidence of severe hypoglycemia will be compared between treatments using Fishers' exact test. The Level 2 and Level 3 are usually considered as clinically significant hypoglycemia. Therefore, the analysis on a composite of Level 2 and Level 3 (denoted as Level 2/3) hypoglycemia will also be conducted.

Table BDCP.1. Hypoglycemia Event Related Analyses

Endpoint	Time Point*	Statistical Method
Rate of hypoglycemia events for Level 1 and Level 2/3 
 • Documented • Nocturnal • Non-Nocturnal 	0-12, 0-26, 12-26 weeks, post-treatment period (up to Visit 801)*	Negative binomial regression with treatment, baseline HbA1c, baseline hypoglycemia incidence for the same type of the dependent variable, log (exposure in year) as the offset in the model.
Incidence of hypoglycemia events for Level 1 and Level 2/3 
 • Documented • Nocturnal • Non-Nocturnal 	0-12, 0-26, 12-26 weeks, post-treatment period (up to Visit 801)*	Logistic regression with treatment, baseline HbA1c, baseline hypoglycemia incidence for the same type of the dependent variable in the model.

 • Proportion of patients with HbA1c <7% without documented nocturnal hypoglycemia event (Level 1 and Level 2) • Proportion of patients with HbA1c $\leq 6.5\%$ without documented nocturnal hypoglycemia event (Level 1 and Level 2) 	0-26 weeks	Logistic regression with treatment, country, baseline HbA1c, and baseline nocturnal hypoglycemia incidence in the model.

Abbreviations: HbA1c = hemoglobin A1c; Level 2/3 = Level 2 and Level 3 composite.

Note: The hypoglycemia rate per year during defined period is calculated by the number of hypoglycemia within the period/number of days patient at risk within the period*365.25 days. The hypoglycemia incidence during defined period indicates if the patient has at least 1 hypoglycemia events within the period (Yes/No). The baseline hypoglycemia rate is the rate calculated between Visit 2 and Visit 3.

*Analyses for endpoint during post-treatment period (up to Visit 801) will include all of the data after study drug discontinuation on Safety population; analyses for endpoints during other time points will include all data before study drug discontinuation on Safety population.

The following is the example of the SAS code of the negative binomial regression for analyzing the rate of hypoglycemia events.

```

proc glimmix empirical data=DATA;
  class TREATMENT;
  model HYPO_FREQ=TREATMENT [BASELINE_HYPO]
    /dist=nb link=log offset=log(exposure in
    days/365.25);
    lsmeans TREATMENT/OM pdiff cl alpha=0.1 ilink;
    random _residual_;
run;

```

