8.3.7.1. Hypoglycemia

Patients will collect information on episodes of hypoglycemia starting from Visit 2 until the last study visit (Visit 801 or ET visit). For that purpose, patients will be trained about signs and symptoms of hypoglycemia, how to treat hypoglycemia, and how to collect in study diaries appropriate information for each episode of hypoglycemia according to the Schedule of Activities (Section 1.3).

Participants will be instructed to report hypoglycemia in the eDiary any time he/she experiences signs or symptoms of hypoglycemia with or without a SMBG ≤ 70 mg/dL (<3.9 mmol/L).

Severe hypoglycemia is defined as an event requiring assistance of another person to actively administer carbohydrate, glucagon, or other resuscitative actions. During these episodes, the participant has an altered mental status and cannot assist in his/her own care, may be semiconscious or unconscious, or experience coma with or without seizures and may require parenteral therapy. Glucose measurements may not be available during such an event, but neurological recovery attributable to the restoration of BG concentration to normal is considered

sufficient evidence that the event was induced by a low BG concentration (≤ 70 mg/dL [<3.9 mmol/L]).

If a hypoglycemic event meets the criteria of severe as confirmed by the investigator, it needs to be recorded as serious on the AE eCRF and reported to Lilly as an SAE.

In each case of suspected or confirmed hypoglycemia, it is important that the event be properly categorized, the effect of the intervention be assessed, and the frequency and duration of hypoglycemia be evaluated. The role of dietary changes and physical exercise (or any other contributing factor) in the development of an event should be established. The patient should receive additional education, if deemed appropriate. Management of increased risk of hypoglycemia is described in Section 6.1.2.2.

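### The two composites of HbA1c target without nocturnal hypoglycemia leave out Level 3, so a participant whose only nocturnal event is severe and has no glucose reading is scored as a success

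*SAP*

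**What the plan says.** SAP 5.10.3.2 sets two levels by glucose concentration. Level 1 is below 70 and at least 54 mg/dL; the other is "Level 2: glucose < 54 mg/dL (3.0 mmol/L"). Documented, documented nocturnal and documented non-nocturnal events are then built on those readings: "With the above glucose reading requirement for Level 1 and 2 hypoglycemia, the following type of hypoglycemia events will be derived". Severe hypoglycemia is a third category, which the cited standard "also classified severe hypoglycemia as Level 3 hypoglycemia". Protocol 8.3.7.1 defines it by the need for help from another person and by altered mental status. It adds "Glucose measurements may not be available during such an event" and accepts neurological recovery once glucose is restored as enough evidence.

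The SAP also creates a Level 2/3 category, because "The Level 2 and Level 3 are usually considered as clinically significant hypoglycemia". In Table BDCP.1 the rate rows use Level 1 and Level 2/3, and so do the incidence rows ("Incidence of hypoglycemia events for Level 1 and Level 2/3"), each with a nocturnal line. The last two rows are the composites. The first is "Proportion of patients with HbA1c <7% without documented nocturnal hypoglycemia event (Level 1 and Level 2"). The second sets the target at or below 6.5% and is likewise "without documented nocturnal hypoglycemia event (Level 1 and Level 2"). Both cover Weeks 0-26 and are analysed by logistic regression. Level 3 does not appear in either.

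Protocol 6.1.2.2, on managing raised hypoglycemia risk, uses the word documented more widely: it takes in any severe case that the investigator has confirmed.

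**The concern.** A composite of this kind is read as the proportion of participants who reached good control without lows at night. A severe night-time event is the clearest way to fail it. As the rows are written, such an event counts only through its glucose value. If there is no value, the event drops out and the participant can be scored as a success, while a participant with a single mild reading is scored as a failure. That ordering is the reverse of clinical seriousness.

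The omission looks unintended. The SAP says that Levels 2 and 3 belong together and combines them everywhere else in the table. At stake is the meaning of two supplementary rows, not the main conclusion of the trial.

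**Working it through.** The documents give no figure for these composites, so there is none to reproduce. The check has two parts.

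**1. Scoring rule applied to test cases.**

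- SAP rule: success = HbA1c below 7% and no nocturnal event with a reading below 70 mg/dL (Level 1 or Level 2).
- Amended rule: the same, and no nocturnal Level 3 event, with or without a reading.

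The HbA1c and glucose values are illustrative.

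| Case | SAP rule | Amended rule |
|---|---|---|
| a. HbA1c 6.8%; severe nocturnal event, no reading | success | failure |
| b. HbA1c 6.8%; severe nocturnal event, reading 45 mg/dL | failure | failure |
| c. HbA1c 6.8%; severe nocturnal event, no reading, plus another nocturnal reading of 65 mg/dL | failure | failure |
| d. HbA1c 7.4%; severe nocturnal event, no reading | failure | failure |
| e. HbA1c 6.8%; non-severe nocturnal reading of 65 mg/dL | failure | failure |

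Only case a changes. All four conditions must hold together: HbA1c at target, a severe nocturnal event, no reading below 70 mg/dL for it, and no other documented nocturnal event in Weeks 0-26. The same logic applies to the 6.5% row.

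**2. Size.**

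*Weight of one participant.* Protocol 9.2 plans about 119 randomized per arm, so one participant is 1/119 = 0.84 percentage points. The 95 per arm in the same section are expected completers. The footnote to Table BDCP.1 places these analyses on the Safety Population (everyone dosed), so 119 is the closer denominator. It is approximate for LY3209590, because that population also pools the former Algorithm 2 participants, whose number is not given. Protocol 9.4.6.3 names the Efficacy Population for hypoglycemia, which also is not limited to completers.

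*Expected number misscored per arm* = 119 × P(severe event) × P(nocturnal) × P(no reading) × P(HbA1c below 7%) × P(no other documented nocturnal event).

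None of the five proportions is in the documents. The ranges below are assumptions, and the factors are treated as independent, which is also an assumption.

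| Input | Low | Middle | High |
|---|---|---|---|
| Severe event | 0.02 | 0.05 | 0.10 |
| Nocturnal | 0.25 | 0.40 | 0.50 |
| No reading | 0.10 | 0.30 | 0.50 |
| HbA1c below 7% | 0.30 | 0.40 | 0.50 |
| No other documented nocturnal event | 0.10 | 0.30 | 0.50 |
| **Expected participants per arm** | **0.002** | **0.086** | **0.74** |

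High column: 119 × 0.10 × 0.50 × 0.50 × 0.50 × 0.50 = 0.74, or 0.74/119 = 0.6 percentage points. Low column: 119 × 0.02 × 0.25 × 0.10 × 0.30 × 0.10 = 0.002.

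**The case against.** **The rows say what they measure.** They name their levels and use the word documented, so a glucose-confirmed composite could be a deliberate choice. It could be, but no reason is given, and it departs from the other rows of the same table and from the SAP's own grouping of Levels 2 and 3.

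**Documented may already include severe cases, through Protocol 6.1.2.2.** The SAP restricts these rows to Levels 1 and 2 in parentheses and ties documented events to a reading. A programmer following the SAP would leave Level 3 out. If the wider meaning was intended, the SAP has to say so.

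**The case will be rare.** This stands. Participants with severe hypoglycemia or unawareness in the 6 months before screening are excluded (Protocol 5.2), CGM is to be worn without interruption (Protocol 5.1), and low-glucose alarms are mandatory (Protocol 8.2.4). These features make a missing reading less likely but do not rule it out: Protocol 8.2.4 foresees technical problems and calibration periods.

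**Severe events are visible elsewhere.** This also stands. They are reported as serious adverse events, listed, compared by Fisher's exact test, and included in the nocturnal Level 2/3 rows. The composites are not among the objectives of either document and carry no success criterion.

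**Stronger readings the documents do not support.** A reader might infer that severe nocturnal events never count as failures. They do when a reading below 70 mg/dL exists, because Level 2 has no clinical exclusion. A reader might also infer that the rule favours LY3209590. The same rule applies to both arms, so the comparison moves only by the difference between arms in misscored participants, and nothing in the documents indicates its sign.

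**Conclusion.** Wrong as written, minor. As the SAP is worded, both composites score as a success a participant at the HbA1c target whose only nocturnal event in Weeks 0-26 is severe and without a reading. That conclusion rests on the wording alone.

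The size rests on assumptions: probably fewer than one participant per arm (0.002 to 0.74 over the ranges shown), with each participant worth about 0.84 percentage points. Within an arm the error can only raise the success proportion. Its direction in the treatment comparison is unknown. The primary HbA1c analysis, the severe-event comparison and the Level 2/3 rate and incidence rows do not change.

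**What to change.** Reword both composite rows of Table BDCP.1 so that success is the HbA1c target *without nocturnal hypoglycemia (Level 1 or Level 2/3), with Level 3 counted as failure whether or not a glucose value exists*. Writing *or* also removes the possible reading that an event at both levels is needed for failure.

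In SAP 5.10.3.2, state whether documented includes investigator-confirmed severe cases, as in Protocol 6.1.2.2, and use the word the same way throughout the table.

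The cost is a short wording change in two rows and one sentence of definition. No new data are needed: confirmed severe events are already recorded as serious adverse events, and the nocturnal Level 2/3 rows already require them to be classified by time of day.
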